Probable: SAE is likely related to the intervention Possible:
SAE may be related to the intervention Unlikely: SAE is
doubtfully related to the intervention Unrelated: SAE is
clearly not related to the intervention

Participants' descriptions of adverse events (incident reports) will be grouped in a reasonable way, counted, and compared by study groups. A designation of "more-common" will be given to events occurring at an incidence of at least 5% in participants assigned to an intervention group, and for which the incidence is at least twice that observed in a comparison group. Staff will be trained to carefully observe participants' reactions to the study protocol and to take appropriate action including support, discontinuance, or referral to additional counseling services, if necessary. Based on previous experience and the current use of these TCU materials with other IRB research projects we have found that such occurrences are rare.

Reporting Timeline

SAEs will be reported to the PI within 24 hours of detection. Within 3 business days, the PI will send a full report on the SAE, including the action taken with regard to continued study participation to the IRB. Non-serious AEs or adverse effects that lead to subject removal from the protocol will be reported to the IRB within 7 business days. The PI will maintain a record of the SAEs, which can be provided to the IRB electronically. The outcome of SAEs also will be reported to NIDA in annual reports. A summary of the SAEs and AEs that occurred during the previous year will be included in the annual progress report to NIDA.

17. Potential Benefits:

Youth participation may result in introspection and problem identification, and promote and improve analytical problem-solving skills and healthy behaviors. From a larger perspective, participation may help to improve the quality of care for JJ- involved youth experiencing drug- related problems, and this may benefit not only the individual by reducing his/her pain and suffering but also by lessening the burden placed on their family and society at large. Formal adaptations of these materials for JJ youth will provide information on the potential usefulness of a highly active and engaging intervention for changing attitudes and intentions with regard to drug- related problems and health risk. We will also gain valuable information about the use of computerized technologies for delivering the intervention. The minimal and potential risks appear reasonable in relation to the anticipated benefits.

18. Compensation:

Compensation will be provided to the youth either in form as a gift or community service credit for each intervention session. Youth will get to decide at the beginning of each session. They can receive \$20 or 3 community service credits for each intervention session. They will also receive \$20 for each follow-up assessment session.

Although we do not consider the token/toy given for participating in the trivia game as compensation, it is worth noting that participants will receive a small token/toy such as a fidget spinner or equivalent in size/cost for participating in the trivia game and getting a certain number of questions correct.

Youth will also be reminded at each session that the project activities will end on August 31st, 2023 and they will be compensated for the activities completed before then.

19. Procedures to Maintain Confidentiality:

Procedures for protection of participant confidentiality will be followed (i.e., Human Subject Certification of all research staff, all data coded with an ID number, identifying information and research data stored in different places under lock and key, electronic data on a secure server without names).

WHAT IS YOUR HORNED FROG NAME?		
Take the first letter of your first name	Then take the month you were born	Finally, take your favorite color
A Glowing	N Purple	January → Horn
B Blue	O Scarlet	February → Claw
C Green	P Glass	March → Eyes
D Orange	Q Black	April → Tooth
E Yellow	R Blood	May → Tail
F Indigo	S Copper	June → Scale
G Violet	T Gray	July → Heart
H Sapphire	U Fire	August → Foot
I Lightning	V Platinum	September → Horn
J Silver	W Iron	October → Scale
K Gold	X Emerald	November → Claw
L Magic	Y Bright	December → Tail
M Venom	Z Stone	

The research design requires that client subjects be linked across assessment completion and to agency records. All participants will be assigned an arbitrary research ID that will be used to link all of their data. Data forms will only be identified with the research ID, personally identifying information will not appear on data forms. The PI will keep a link file linking names and research IDs on a secure server that does not contain other data. The assessments are intended to be administered online using Qualtrics. The RA will prepare the online assessment, which the participant will access by using a personalized link that is connected with their unique participant ID.

In order to personalize the virtual intervention and app experience, at the beginning of the first session, the RA will log the youth into the system using the client research id, the client will be asked to create their own unique user name, called a “FROG NAME.” Similar to the games on social media that provide users with a formula for creating fantasy names (see image to right), the youth will be presented with a formula to create their Horned FrogName.

For example:

First letter of your first name: R=Tangerine Month you were born: April=Canvas Favorite color: Black=17 Your FROG NAME is: TangerineCanvas17

On subsequent intervention sessions, the youth, once logged in by the RA, will be greeted with their unique frog name (e.g., “Hello TangerineCanvas17!”) while completing the virtual intervention session.

TCU computers are secured by redundant firewall and password access (to both the network domain and email user accounts). Procedures for confidentiality will include de-identified data to assure confidentiality. The general policy adopted by the present investigators is based on those used successfully for many years in other similar projects. Research files at the TCU Institute of Behavioral Research (IBR) do not include the names of the subjects involved in studies. In accordance with standard procedures used by the IBR, the confidentiality and privacy of client information will be protected by well-planned and comprehensive procedures. Only unique code numbers assigned by program staff during

the project will identify all research records. The data files that are created and retained for research will remain anonymous and are entered into computer research files for analysis with only the code numbers as identification. Reports issued will never include subject-level information that could be linked to any individual, and all published data and reports will be based on aggregate information. Participants will be informed that they can choose not to answer uncomfortable questions in order to minimize potential discomfort when responding to survey questions or intervention material. Furthermore, information provided as part of the study will not be shared with participating probation department, including any reported drug use.

This research is covered by a Certificate of Confidentiality from the National Institutes of Health. The researchers may not disclose or use information that may identify a person in any federal, state, or local civil, criminal, administrative, legislative, or other action, suit, or proceeding, or be used as evidence. The Certificate of Confidentiality will not be used to prevent disclosure as required by federal, state, or local law such as, but not limited to child abuse and neglect, or harm to self or others.

Data shared with the research team by TCJS and TJJD will be transmitted via Box.com through a secure file-sharing folder that only the appropriate parties have access to. PID and headquarter county numbers will be shared with TJJD to identify the data needed. Files connecting youth to their PID will be kept secure on TCU- owned shares accessible by the PI. Once data are shared, they are stored on TCU- owned shares that are protected by firewalls and passwords. Any additional security measures requested by the department or TJJD, such as scrambling PID numbers upon receipt of the data will be outlined in subsequent data sharing agreements and followed.

20. Data Analyses:

Implementation feasibility measures will be recorded, summarized, and reviewed monthly by the PI and team in order to inform real-time protocol adjustments (e.g., changes in recruiting practices if target numbers are not reached). Once the targeted youth recruitment goal has been achieved, psychometric properties of baseline measures will be conducted (means, SD, coefficient alpha, exploratory/confirmatory factor analysis). Because the design calls for repeated measures at baseline, month 1, and month 3, measures will not be revised between administration points.

However, psychometrics (conducted on data from all time points) will be used to inform modifications prior to a full-scale R01 RCT and reliability of scales for use in exploratory analyses of intervention efficacy.

Baseline characteristics will be included as covariates in analyses. The distal outcome will be the percent of study subjects who use drugs (self-report, corroborated with positive urine test) at follow-up (1- and 3-months). All study participants (regardless of study retention) will be included in analyses (i.e., an intent-to-treat approach; ITT). Baseline variables that directly relate to our aims (e.g., drug use, risky sex practices) will be evaluated for use as covariates. Abstinence at each

follow-up time point will be compared using chi square test. Our proximal outcomes will include putative measures (e.g., problem recognition, decision making, intention to reduce personal risk) and receipt of SU services (dichotomous measure from youth records). Because proportions of females and their SU rates are generally lower among JJ youth compared to males,⁶ and males/females may respond differently to MEC interventions,¹⁶ we will explore sex (as a biological variable) differences in SU, risky sex practices, and exploratory outcomes using univariate analyses (e.g., chi square, t-tests, ANOVA). We will also explore potential racial/ethnic disparities in order to more fully inform whether cultural modifications are needed for a subsequent application. A log rank test will be used to assess intervention dropout. Participants who withdraw consent or are lost to follow up will be missing on outcome measures. To address this, stochastic multiple-imputation will be attempted, which will provide maximum likelihood estimates, account for uncertainty in missing values, and provide unbiased estimates of the treatment effect if data are missing at random. Effect sizes will be used to calculate sample sizes needed for the larger R01. Calculations will include samples needed to assess intervention feasibility across sex and race/ethnicity subgroups.

21. Check List for the Items That Need to be Submitted:

a. Protocol	
b. Consent document	
c. HIPAA form if applicable	
d. Protecting Human Research Participants Training certificate for each investigator	
e. Recruitment flyers, letters, ads, etc.	
f. Questionnaires or other documents utilized in screening and data collection	

Principal Investigator Assurance

22. By signing below, I certify to the following:

- The project described herein will be conducted in accordance with applicable TCU policies and procedures, as determined by the IRB of record. All Human Subject Research projects occurring at TCU must be conducted in compliance with the Office of Human Protection ("OHRP") regulations at 45 CFR 46 and all other applicable federal and state laws and regulations (collectively "Applicable Law")
- I have a working knowledge of Applicable Law

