courts at hearings, or the duration of the youth's supervision; and that in contrast to court-mandated participation in conditions of the youth's probation, this study is completely voluntary. We will also inform the family that while we will not inform their Probation Officers about their participation, we cannot fully guarantee that they will not learn about their participation through internal JJ communication or in the case the youth discloses their participation to their probation officer. (2) To ensure that both caregivers and youth understand the study and all it entails, the RA will assess their comprehension by asking them "what is the purpose of the study", "what are the risks of the study", and "what will happen if you choose not to participate". If the youth and caregiver are unable to answer or they respond incorrectly, the RA will go over the applicable study components again. This will be repeated until the youth and caregiver understand the study and its associated risks.

Due to using Qualtrics to obtain informed consent, a waiver of signed informed consent request was approved by the IRB in the initial project submission (see Appendix 8). It was stamped & approved by the IRB on 1/13/21 and uploaded into Cayuse for AM2 to bring files up to date.

15. Study Procedures:

Procedures

The project ends on 8/31/23 and no sessions will occur past this date. Youth and Caregivers will be informed during consent and assent (verbally and written), that the project ends on 8/31/23. Project referrals will cease on 05/31/2023 to allow clients an opportunity to participate in all study activities prior to project end.

If consent is completed first, the RA will schedule the first session with the youth and perform the assent process at the start of the session and assessment after. The RA will provide the youth with up to 3 reminder e-mails and text message before the session to ensure the youth has log-in information if required, or address of the agreed location to meet. They will also be reminded of the day and time of meeting. See appendices 3 for email and text scripts.

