Following assent and assessment the youth will receive a tablet to use during the study. The RA will walk through a tutorial with youth to ensure they learn how to use the tablet. The youth will then have the first intervention session with the RA. The RA will complete administrative procedures to ensure the youth is presented with the correct modules for the session, and the youth will complete the session independently with the RA available to answer questions. Once the youth completes the session, they will complete an end of session evaluation (using Qualtrics), and the RA will transition the youth out of the session and schedule the next session or the follow-up assessment (following the 4th session of the intervention).

The first intervention session will occur approximately a week after the consent/assent meeting, and each session will occur a week to several weeks apart (spanning across approximately 1 month).

Following the last session, the youth will be scheduled to complete a 1-month assessment either in-person or online with the RA. The youth will receive 2 reminder e-mails and text messages leading up to the assessment appointment. The youth will also complete a 3- month post- intervention assessment proctored virtually or in-person by the RA. The youth will also receive 3 reminder e-mails and text messages leading up to the final assessment. Reminder e-mails will come from the e-mail address [contact] with the subject line "SUHRI Reminder" directly to the youth's personal e-mail address to reduce the chance that another individual will see the e-mails. No reference to a research project will be made in the text.

Each follow-up assessment will last approximately 60 minutes, with intervention sessions lasting approximately 60 – 90 minutes each.

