Each session includes two modules including a WORK-IT module where youth will work through a scenario they select using the WORK-IT framework. The other module includes two interactive games; the Escaping the Downward Spiral (EDS) game and Jeopardy style trivia. In the EDS game, youth will play a game that focuses on decision-making in scenarios involving substance use and sex, while in the Jeopardy style game, they will learn about facts around substance use and risky sexual decision-making. Participants may receive a small token (e.g., fidget spinner or equivalent toy of size/cost) if they answer a certain number of questions correctly in the trivia game at the end of the intervention sessions. If the last session is virtual, RAs will offer to mail the token to participants and request their mailing address to do so. The tokens will be mailed with a "congratulations" leaflet (Appendix 12) that congratulates the participant on winning the trivia and requests them to be on the lookout for a follow-up survey (the assessment session). Intervention sessions will last approximately 60 - 90 minutes. The youth will complete these independently on a tablet/computer but the RA will be available in-person or via virtual platform to proctor participation. Modules also include the provision of additional information and service information related to substance use and risky sex practices.

Assessment

Participants will be asked to complete a battery of assessments at baseline, 1-month post-baseline, and 3 months post baseline. The assessment/measures package has been approved in several submissions across the initial study submission, AM 1, AM 2, AM 4, and AM6. Participants will also be asked to complete post-session feedback for each intervention session (approved on AM 2 & AM4).

Compensation / Community Service Hours

Compensation will be provided to the youth either in form as a gift card or community service

credits for each intervention session. Youth will get to decide at each session if they want to receive a gift card or community service credit. They can receive \$20 or 3 community service credits for each intervention session. They will also receive \$20 for each follow-up assessment session. Youth will also be reminded at each session that the project activities will end on August and they will be compensated for the activities completed before then.

16. Potential Risks and Precautions to Reduce Risk:

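### The 3-month assessment is anchored to the end of the intervention in one place and to baseline in another; on the post-intervention clock the 05/31/2023 referral cut-off falls 13 to 37 days short

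*Combined protocol and SAP*

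**What the plan says.** The Procedures text of section 15 sets a hard stop: "The project ends on 8/31/23 and no sessions will occur past this date". It then sets the referral cut-off and its purpose: "Project referrals will cease on 05/31/2023 to allow clients an opportunity to participate in all study activities prior to project end".

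The same text gives the sequence of visits. On the start: "The first intervention session will occur approximately a week after the consent/assent meeting". On spacing: "each session will occur a week to several weeks apart (spanning across approximately 1 month". There are four sessions. On the last visit: "The youth will also complete a 3- month post- intervention assessment proctored virtually or in-person by the RA". The 1-month assessment is scheduled after the last session, but its starting point is not stated.

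The Assessment text, also in section 15, uses a different clock: "Participants will be asked to complete a battery of assessments at baseline, 1-month post-baseline, and 3 months post baseline". Section 20 (Data Analyses) is consistent with that one: "the design calls for repeated measures at baseline, month 1, and month 3".

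Baseline may fall at session 1. Where consent is completed first, the research assistant is to "perform the assent process at the start of the session and assessment after".

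No visit window and no referral-to-consent interval is given.

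**The concern.** The two section 15 texts give different due dates for the same assessment. The cut-off rule can only be judged once one of them is chosen. If the post-intervention clock governs, the rule cannot do what it says it is for: a youth referred near the cut-off reaches the 3-month date after the project has closed.

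Subject retention is a stated aim of Pilot 2 (Summary). Section 20 names withdrawal of consent and loss to follow-up as the sources of missing outcomes. It has no category for follow-up cut short by project end, and it does not define the retention denominator. A late-referred youth would either miss the assessment because of the calendar or have it early, and nothing says whether an early one counts. If such youth were counted as not retained, closure of the project would be mixed with dropout.

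**Working it through.** **Time available.** The plan gives two dates and no day count. From 31 May to 31 August 2023 is 30 + 31 + 31 = 92 days, or three calendar months.

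**Inputs from section 15.**
- Consent to session 1: about 7 days.
- Session 1 to session 4: three gaps. Weekly gaps give 21 days; the stated span of about a month is taken as 30.
- Three months: 91 to 92 days, or 84 if read as 12 weeks.
- Referral to consent: not given. Assumed 0 days, which favours the plan.

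**Post-intervention clock:** consent gap + session span + 3 months.

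| Reading | Days needed | Short of 92 by |
|---|---|---|
| Weekly sessions, 91 days | 7 + 21 + 91 = 119 | 27 |
| One-month span, 92 days | 7 + 30 + 92 = 129 | 37 |
| Weekly sessions, 12 weeks | 7 + 21 + 84 = 112 | 20 |
| One-month span, 12 weeks | 7 + 30 + 84 = 121 | 29 |
| Session 1 on consent day, weekly, 12 weeks | 0 + 21 + 84 = 105 | 13 |

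For a referral on 31 May, 119 to 129 days puts the due date between 27 September and 7 October 2023. The latest referral that fits is 4 May (119 days) or 24 April (129 days).

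**Post-baseline clock:** days to baseline + 3 months.

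| Reading | Days needed | Against 92 |
|---|---|---|
| Baseline on referral day, 12 weeks | 0 + 84 = 84 | 8 spare |
| Baseline on referral day, 91 to 92 days | 91 to 92 | 1 to 0 spare |
| Baseline at session 1, 12 weeks | 7 + 84 = 91 | 1 spare |
| Baseline at session 1, 91 to 92 days | 7 + 91 = 98 to 7 + 92 = 99 | 6 to 7 short |

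In the last row, the latest referral that fits is 25 or 24 May.

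**Scheduling lag.** Each day between referral and consent adds a day to every row. With a lag of 7 to 14 days (assumed), the post-intervention total becomes 119 + 7 = 126 to 129 + 14 = 143. The most favourable post-baseline total becomes 84 + 7 = 91 to 84 + 14 = 98.

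**Gap between the clocks.** With baseline at session 1, the due dates differ by the session span, 21 to 30 days.

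**Earlier visits.** With a one-month span, the four sessions and a 1-month post-intervention visit take 7 + 30 + 30 = 67 days and fit. With gaps of three weeks, which the text permits if several weeks can mean three, they take 7 + 63 + 30 = 100 days and do not.

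**If the last visit is brought forward.** Consent on 31 May and session 1 on 7 June put session 4 on 28 June (weekly) or 7 July (one-month span). An assessment on 31 August is then 64 or 55 days after session 4.

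**Effect on retention.** In the worst case, each youth counted as not retained for this reason lowers 3-month retention by 1/60 = 1.7 percentage points, with the expected 60 youth.

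**The case against.** The best defence is that the Assessment text is the dedicated statement of timing, that section 20 agrees with it, and that 31 May to 31 August is exactly three months. If that text governs, the large shortfall disappears. Baseline at session 1 is also conditional on consent coming first, since section 13 plans consent and assent at one initial meeting. This stands: the root of the problem is the anchor, and the cut-off is a consequence. It does not clear the plan, because the Procedures text still says otherwise and the post-baseline fit leaves 8 days at best before any lag.

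The intervals are approximate, and the rule promises only an opportunity. But dropping the consent week, using weekly sessions and counting 12 weeks still leaves the post-intervention clock 13 days over, so a youth referred on 31 May has no opportunity for an on-time visit.

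The plan also softens the consequence: families are told the end date, youth are paid for activities completed before it, and section 20 provides monthly feasibility review. These help but do not close the gap.

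A reader might infer that the cut-off fails on any reading, or that the outcome analyses are compromised. The documents support neither. Some post-baseline readings fit. Section 20 includes all participants and plans multiple imputation, and missingness set by a calendar date is a plausible case of missing at random. The log-rank test of intervention dropout concerns the sessions and is not exposed to a missed 3-month visit. Nor do the documents say that truncated youth would be counted as dropouts; they leave it open.

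**Conclusion.** The point holds as a minor internal inconsistency. Section 15 gives two anchors for the final assessment. On the post-intervention anchor the referral cut-off misses its stated purpose by 13 to 37 days, so the last 2 to 5 weeks of referrals cannot be assessed on time. On the post-baseline anchor the cut-off is marginal, from 8 days spare to 7 days short. All these figures assume no lag from referral to consent.

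The four sessions and the 1-month visit fit only if the sessions keep to about a month; a reader should not assume that they always fit.

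The number of youth affected cannot be computed, because no referral rate is given. As an illustration only, assume even enrolment of 60 youth over the 868 days from the IRB approval date of 1/13/21 to 5/31/23. Then 60 × 13/868 = 0.9 to 60 × 37/868 = 2.6 youth would be affected. A shorter enrolment period would give more.

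**What to change.** 1. Reconcile the Procedures and Assessment texts of section 15 to one follow-up anchor, and state a visit window for the 3-month assessment.
2. Check the cut-off against that anchor, then do one of the following.
   - Move it earlier: to about 5/24/2023 for a post-baseline anchor with baseline at session 1, or to about 4/24 to 5/4/2023 for a post-intervention anchor. In either case subtract the expected scheduling lag.
   - Keep it, and compute 3-month retention among youth whose consent date leaves enough calendar time for the planned schedule (the same dates, applied to consent). Report the others as administratively censored by project end, not as dropout.
3. Under either option, keep all youth in the outcome analyses under the stated all-participants rule and multiple imputation.

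The cost is small. Moving the cut-off gives up between one and about five weeks of referrals, with their session and 1-month data. Keeping it makes the 3-month retention denominator slightly smaller and changes no outcome analysis.

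As a separate editorial correction, section 13 still gives the project end as 8/31/22, against 8/31/23 in sections 15 and 18.

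### The final assessment is timed from the end of the intervention in one place and from baseline in another, at least 21 days apart for completers, and the referral cutoff leaves little or no time on either clock

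*Combined protocol and SAP*

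**What the plan says.** Section 15 (Study Procedures) contains both timings. The Assessment subsection counts from baseline: "Participants will be asked to complete a battery of assessments at baseline, 1-month post-baseline, and 3 months post baseline". The Procedures subsection says of the final visit: "The youth will also complete a 3- month post- intervention assessment proctored virtually or in-person by the RA". On the first follow-up it says: "Following the last session, the youth will be scheduled to complete a 1-month assessment either in-person or online with the RA". This fits its instruction that, when a session ends, the research assistant should "schedule the next session or the follow-up assessment (following the 4th session of the intervention".

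The same subsection gives the session schedule. Session 1 is planned for about seven days after consent and assent. On the spacing of sessions it states: "each session will occur a week to several weeks apart (spanning across approximately 1 month". When consent comes first, assent and then the assessment are done at the start of the first session.

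On the calendar, Procedures states: "The project ends on 8/31/23 and no sessions will occur past this date". It also states: "Project referrals will cease on 05/31/2023 to allow clients an opportunity to participate in all study activities prior to project end". Section 18 repeats the August 31st, 2023 end of activities.

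Section 20 (Data Analyses) takes the distal drug-use outcome and the abstinence comparison at 1 and 3 months, and refers to month 1 and month 3 without saying what the months count from. It includes every participant whatever their retention, and will use the effect sizes to size a later R01.

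**The concern.** Baseline comes before session 1, so three months after baseline and three months after the intervention cannot be the same day for anyone who completes four weekly sessions. Both statements are in current text of the same section, and the analysis section does not choose between them. A research assistant working from Procedures could reasonably book the last visit about three months after session 4. One working from Assessment would book it several weeks earlier.

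If both happen, results labelled 3-month mix different lengths of follow-up, and so do the effect sizes carried into the R01. Subject retention is a stated aim of Pilot 2, and it cannot be scored consistently without a single due date. On the post-intervention clock, a youth who stops before session 4 has no due date at all, yet stays in the analysis. The referral cutoff exists so that all activities fit before project end, and whether it does that depends on the clock.

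**Working it through.** The plan gives no figure of its own to reproduce, so the check is calendar arithmetic on its schedule.

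**Inputs from the plan**
- Four sessions, so three intervals, each at least 7 days; total span about one month (Section 15).
- Session 1 about 7 days after the consent/assent meeting (Section 15).
- Last referral 31 May 2023; project end 31 August 2023 (Section 15; end date also in Section 18). Section 13 still gives 8/31/22 as the end; that is a separate inconsistency and is not used here.

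**Assumptions**
- One month is 30 days. Three months is 91 days or three calendar months, with 84 days as a favourable extreme.
- Session span is 21 days (3 × 7) or 30 days.
- Consent is on the referral date.
- Baseline is at session 1 (b = 0). An earlier baseline at the consent/assent meeting (b = 7) is a sensitivity case.

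**Step 1: gap between the clocks.** For a completer, gap = b + span, which is also the day of session 4 counted from baseline. Days from session 4 to a month-3 visit timed from baseline = 91 − gap. Month 1 relative to session 4 = 30 − gap.

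| b | span | gap (days) | session 4 to baseline-timed month 3 | baseline-timed month 1 relative to session 4 |
|---|---|---|---|---|
| 0 | 21 | 21 | 70 | 9 days after |
| 0 | 30 | 30 | 61 | same day |
| 7 | 21 | 28 | 63 | 2 days after |
| 7 | 30 | 37 | 54 | 7 days before |

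On the post-intervention clock, month 3 would be 91 days after session 4 in every row.

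**Step 2: time available.** 31 May to 31 August 2023 = 30 + 31 + 31 = 92 days.

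**Step 3: post-intervention clock, last-day referral.**
- Weekly sessions: 7 + 21 + 91 = 119 days, giving 27 September; 119 − 92 = 27 days late.
- One-month span: 7 + 30 + 91 = 128 days, giving 6 October; 128 − 92 = 36 days late.
- Calendar months add one day: 28 September and 7 October, 28 and 37 days late.
- Most favourable case (session 1 on the referral day, 21-day span, 84 days): 0 + 21 + 84 = 105 days; 105 − 92 = 13 days late.

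**Step 4: baseline clock, last-day referral.**
- Baseline on 31 May: 91 days gives 30 August (1 day spare); three calendar months gives 31 August (0 spare).
- Baseline at session 1 on 7 June: 91 days gives 6 September (6 days late); calendar months gives 7 September (7 days late).
- With 84 days the visit fits in both cases, by 8 days and 1 day.

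**The case against.** The best defence is that post-intervention is only a phase label. The Data and Safety Monitoring Plan calls baseline the pre-intervention assessment and speaks of a post-intervention assessment in the same way. The cutoff supports this: 31 May to 31 August is exactly three calendar months, which suggests that the baseline clock was intended. It does not prove it. No passage defines the term as a label, Procedures attaches the three months directly to it, and on the baseline clock the cutoff works only if baseline is done almost on the referral day or three months is counted short.

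A second defence is that truncated follow-up is anticipated: the cutoff offers an opportunity rather than a guarantee, youth are paid for what they complete before the end, and missing outcomes are to be imputed. This softens the consequence for late referrals but does not say when the visit is due.

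Three stronger readings are tempting and should not be made:
- A reader might infer that month 1 has no anchor. It has one: Assessment states post-baseline. Procedures says only that the visit follows the last session. The difficulty is that at a one-month span the two nearly coincide, and their order reverses if sessions run longer, or if a one-month span is combined with a baseline a week earlier.
- A reader might infer that month-1 visits will fall before session 4. With baseline at session 1 and a span of 30 days or less, none does.
- A reader might infer that only the post-intervention clock runs out of time. Step 4 shows that the baseline clock has almost no slack either.

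**Conclusion.** The conflict stands. The visit that carries the distal outcome has two time origins, at least 21 days apart for completers, about 30 days at the stated span, and about a week more if baseline is done at an earlier consent/assent meeting. Longer session spacing, which the plan allows, would widen this.

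For a last-day referral, the final visit misses project end by about 27 to 37 days on the post-intervention clock, and by at least 13 days under the most favourable assumptions tried. On the baseline clock there is 0 to 1 day spare, or it is 6 to 7 days late with baseline at session 1 a week after consent. These dates assume consent on the day of referral; any lag makes them worse.

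On the post-intervention clock the shortage affects roughly the last two to five weeks of referrals. The number of youth is unknown because no accrual rate is given. The documents do not show that visits have been held on mixed clocks, and the consent forms and measures package, which may state the timing, are not in the reviewed text. For a feasibility pilot with exploratory efficacy analyses, this should be fixed but does not threaten the study.

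**What to change.** 1. Reconcile the Procedures and Assessment subsections of Section 15 and the month labels in Section 20 to one named anchor for both follow-ups, with a visit window. Check that the consent and assent forms agree.
2. Make the referral cutoff or the window consistent with that anchor, or state that later enrollees have no month-3 visit and are not counted as lost to follow-up. On the baseline clock, a month-3 window that opens by day 85 would cover a 7 June baseline (7 June + 85 days = 31 August).
3. If the post-intervention anchor is kept, give youth who stop before session 4 a due date, for example from the scheduled date of session 4.
4. At each assessment record days since baseline, days since last session and sessions completed, and report the 1- and 3-month outcomes with that timing. This is worth doing even for visits already held.

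The cost is a short amendment and three timing variables, plus relabelling of any assessment done on the other clock. The baseline anchor may cost about a week of late referrals unless the window absorbs it. The post-intervention anchor costs about the last 27 to 37 days of referrals, or the month-3 visits of those youth.
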